### **2.2.2. Clinical Overview**

As of the protocol date, 3 clinical studies, C3421001, C3421002, and C3421003 have been completed dosing with PF-06882961. C3421001, which administered single ascending oral doses of PF-06882961 or placebo to healthy adult participants, C3421002, which administered multiple ascending oral doses of PF-06882961 or placebo to adults with T2DM and safety results from this study are provided in Section 2.2.2.1, and C3421003, which administered single oral doses of different formulations of PF-06882961 to healthy participants. Refer to the IB for more details on these studies and the known drug class effects of marketed injectable GLP-1R agonists.

#### **2.2.2.1. Clinical Safety**

Clinical data from the completed C3421001, C3421002 and C3421003 studies are provided in the IB for PF-06882961.

The results of C3421002, which is the only completed multiple dosing study in patients with T2DM to date, are summarized as below.

In Study C3421002, PF-06882961 doses ranging from 10 mg BID to 120 mg BID were generally safe and well tolerated. A total of 98 participants with T2DM on a background of metformin were randomized to receive PF-06882961 or matching placebo in a 3:1 randomization ratio, and 92 participants completed the study. Six (6) participants discontinued from the study, of which 2 discontinuations were due to treatment-related TEAEs, and 4 withdrew during the treatment or follow-up period for non-treatment related reasons. One (1) participant in the 15 mg BID group discontinued from the study due to a treatment related, moderate TEAE of headache on Day 2. One (1) participant in the 50 mg BID group discontinued from the study due to moderate TEAEs of decreased appetite on Day 1, nausea, vomiting, and a mild TEAE of fatigue on Day 7 (all related to study drug).

A total of 319 TEAEs were reported, of which the majority of the AEs [294 (92%)] were mild in intensity, 23 (7%) were moderate, and 2 (1%) were severe in intensity. The most frequently reported TEAEs were nausea (49.0%), dyspepsia (32.7%), vomiting (26.5%), diarrhea (24.5%), headache (23.5%), and constipation (20.4%). One (1) participant

experienced a TEAE of hypoglycemia. This AE was non-fasting, mild in severity and of limited duration.

No deaths occurred in the C3421002 study. Two (2) participants experienced 2 severe TEAEs during the study, 1 of which occurred in the dosing period and was considered treatment related, the other occurred during the follow-up period and was not considered treatment related. The latter participant experienced 2 non-treatment-related SAEs, 1 of which occurred in the follow-up period and was a TEAE of severe intensity, and the other occurred outside of the study reporting period.

While there were isolated values for laboratory tests, vital signs and ECG intervals outside of the reference ranges, no clear adverse trends were apparent in these parameters. As has been reported for marketed GLP-1R agonists, increases in heart rate have been observed, with mean increases ranging from 5 to 15 bpm across doses administered to date, and most heart rate values were within the normal range. In summary, PF-06882961 was generally safe and well tolerated in C3421002, with a safety profile in line with marketed GLP-1R agonists.

#### **2.2.2.2. Clinical Pharmacokinetics**

The clinical PK of PF-06882961 in healthy adult participants has been evaluated in two completed studies: C3421001 and C3421003. The results of these completed studies are summarized in the PF-06882961 IB.

The PK properties of PF-06882961 have been evaluated in adult participants with T2DM as part of the completed C3421002 study. In this study, the first 6 cohorts received PF-06882961 or placebo dosed BID. Dosing for 4 of the 6 cohorts was titrated for various amounts of time over the 28 days, with target maximum doses ranging between 10 and 120 mg BID across the 6 cohorts. Approximately dose proportional increases in  $C_{max}$  and  $AUC_{24}$  were observed between the doses of 10 mg BID and 120 mg BID, with geometric mean  $C_{max}$  ranging from 38.38 to 685.2 ng/mL and  $AUC_{24}$  ranging from 455.9 to 8368 ng•h/mL. Percent coefficients of variance (%CV) ranged from 32 to 94 and 41 to 87 for  $C_{max}$  and  $AUC_{24}$  respectively on Day 28. Consistent with data from the completed studies, PF-06882961 was observed to have a  $t_{1/2}$  of approximately 4.681 to 8.090 hours. Median  $T_{max}$  ranged from 3 to 6 hours after the AM dose over the dose ranges administered.

### **2.3. Benefit/Risk Assessment**

More detailed information about the known and expected benefits and risks and reasonably expected AEs of PF-06882961 may be found in the IB, which is the SRSD for this study.

### 2.3.1. Risk Assessment

Potential Risk of Clinical Significance	Summary of Data/Rationale for Risk	Mitigation Strategy
Study Intervention(s) PF-06882961		
Thyroid C-cell tumors	
The potential risks are based on product labeling for injectable GLP-1R agonists (ie, liraglutide, dulaglutide, and exenatide) due to dose-dependent and treatment duration-dependent thyroid C-cell tumors in nonclinical studies in rats and mice at clinically relevant exposures.
 
Thyroid C-cell tumors have not been observed with PF-06882961 in clinical or nonclinical studies.
	
Potential participants with a personal or family history of medullary thyroid carcinoma or MEN2 are excluded from the clinical development program. Thyroid function tests are included in the clinical trial protocols to monitor participants' thyroid function.

Pancreatitis	
The potential risks are based on product labeling for injectable GLP-1R agonists (ie, liraglutide, exenatide and dulaglutide).
 
Pancreatitis has not been observed in the PF-06882961 clinical trial program.
	
Per exclusion criteria, potential participants with acute pancreatitis or a history of pancreatitis are not eligible for study entry. Serum amylase and lipase are monitored during the clinical studies.

Hypoglycemia	
Clinical trials with injectable GLP-1R agonists have not demonstrated an increased risk for hypoglycemia. However, when administered in combination with anti-diabetic agents that are known to have an increased risk of hypoglycemia (such as insulin or sulfonylureas), an increased risk for hypoglycemia was observed.
 
Only one adverse event of mild hypoglycemia has been reported in the clinical development program to date.
	
Blood glucose is monitored frequently during clinical studies involving patients with T2DM, and hypoglycemia is a well recognized risk in T2DM patients. The IB and ICD inform of the potential increased risk of hypoglycemia when PF-06882961 is administered in combination with anti-diabetic agents that are known to have an increased risk of hypoglycemia (such as insulin or sulfonylureas), which are prohibited in this study.

Impairment in renal function	
In rats, minimal renal tubular vacuolation was observed, but this finding was considered to be non-adverse.
	
Per exclusion criteria, potential participants with significant renal impairment (<60 mL/min/1.73m^2) are not eligible for study entry. Renal function is

Potential Risk of Clinical Significance	Summary of Data/Rationale for Risk	Mitigation Strategy
	In the clinical trial program only one mild AE (Blood creatinine increased) has been observed.	monitored during the study by the lab assessments of serum BUN, creatinine and eGFR.
Gastrointestinal adverse reactions	
The potential risks are based on product labeling for injectable GLP-1R agonists (ie, liraglutide, exenatide and dulaglutide).
 
In addition, gastrointestinal AEs, the majority of which were mild in severity, have been observed in the clinical program with PF-06882961. In nonclinical studies with PF-06882961, gastrointestinal adverse effects have been seen in rats and monkeys.
	
Participants are monitored during the clinical study visits, via body weight, vitals signs and laboratory assessments, to prevent potential sequelae of any severe gastrointestinal reactions, eg, dehydration.
 
Dose titration will be adopted to enhance tolerability to PF-06882961.

Diabetic retinopathy complications	
The potential risk is based on the product labeling for the injectable GLP-1R agonist semaglutide for T2DM. This risk has not been listed in the prescribing information for other marketed GLP-1R agonists.
 
There are no nonclinical or clinical data involving PF-06882961 to suggest an increased risk of diabetic retinopathy complications.
	Potential participants with a known medical history of active proliferative retinopathy and/or macular edema are excluded from the clinical studies.
Use of a placebo arm.	Participants randomized to placebo may not experience glycemic lowering effect.	
A majority of the randomized study population will receive PF-06882961, and all participants will receive lifestyle counseling, which is standard of care for management of T2DM.
 
Participants will be actively monitored and those who experience hyperglycemia, per protocol defined criteria, may be discontinued and receive rescue medication.

Potential Risk of Clinical Significance	Summary of Data/Rationale for Risk	Mitigation Strategy
Other		
During the COVID-19 pandemic, the following is recommended: Risk COVID-19 contamination during study.	During the pandemic participant could be infected with the the SARS-COV-2 virus through study participation. This could lead to increased health risk for this participant and others in the study.  Confounding AE with compound.	COVID-19 specific assessments according to SoA .

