### 5. STUDY POPULATION

This study can fulfill its objectives only if appropriate participants are enrolled. The following eligibility criteria are designed to select participants for whom participation in the study is considered appropriate. All relevant medical and nonmedical conditions should be taken into consideration when deciding whether a particular participant is suitable for this protocol.

Prospective approval of protocol deviations to recruitment and enrollment criteria, also known as protocol waivers or exemptions, is not permitted.

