### **Medical Conditions:**

1. Evidence or history of clinically significant hematological, renal, endocrine, pulmonary, gastrointestinal, cardiovascular, hepatic, psychiatric, neurological, or allergic disease (including drug allergies, but excluding untreated, asymptomatic, seasonal allergies at the time of dosing).
  - Patients who have chronic conditions other than T2DM (for example, hypercholesterolemia or hypertension) but are controlled by either diet or stable doses of medications may be included (for example, a participant with hypercholesterolemia on appropriate treatment is eligible).
2. Any condition possibly affecting drug absorption (eg, prior bariatric surgery, gastrectomy, or any area of intestinal resection, active inflammatory bowel disease or pancreatic insufficiency).
3. Diagnosis of type 1 diabetes mellitus or secondary forms of diabetes.
4. History of myocardial infarction, unstable angina, arterial revascularization, stroke, New York Heart Association Functional Class II-IV heart failure, or transient ischemic attack within 6 months of Screening (Visit 1).
5. Any malignancy not considered cured (except basal cell carcinoma and squamous cell carcinoma of the skin); a participant is considered cured if there has been no evidence of cancer recurrence in the previous 5 years.
6. Personal or family history of medullary thyroid carcinoma (MTC) or multiple endocrine neoplasia syndrome type 2 (MEN2), or participants with suspected MTC per the PI's judgement.
7. Acute pancreatitis or history of chronic pancreatitis.

8. Acute gallbladder disease.
9. History of human immunodeficiency virus (HIV), hepatitis B, or hepatitis C; positive testing for HIV, hepatitis B surface antigen (HBsAg), hepatitis B core antibody (HBcAb), or hepatitis C antibody (HCVAb) or syphilis. Hepatitis B vaccination is allowed.
10. Known intolerance or hypersensitivity to GLP-1R agonists.
11. Other medical or psychiatric condition including recent (within the past year) or active suicidal ideation/behavior or laboratory abnormality or other conditions or situations related to COVID-19 pandemic that may increase the risk of study participation or, in the investigator's judgment, make the participant inappropriate for the study.

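### Protocol Section 2.3.1 relies on entry exclusions for retinopathy/macular edema and for any history of pancreatitis that Section 5.2 does not contain, or contains only in narrower form

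*Protocol*

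**What the plan says.** Protocol Section 2.3.1 pairs each potential risk with a mitigation.

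- **Retinopathy row.** The mitigation is a single sentence: "Potential participants with a known medical history of active proliferative retinopathy and/or macular edema are excluded from the clinical studies". On the evidence for the risk, the row says: "There are no nonclinical or clinical data involving PF-06882961 to suggest an increased risk of diabetic retinopathy complications". It bases the risk on the labeling of another GLP-1R agonist.
- **Pancreatitis row.** "Per exclusion criteria, potential participants with acute pancreatitis or a history of pancreatitis are not eligible for study entry". The row adds amylase and lipase monitoring.

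Protocol Section 5.2 is the list that the site applies.

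- **Criterion 7:** "Acute pancreatitis or history of chronic pancreatitis".
- **Criterion 1** is a general organ-system exclusion: "Evidence or history of clinically significant hematological, renal, endocrine, pulmonary, gastrointestinal, cardiovascular, hepatic, psychiatric, neurological, or allergic disease". The eye is not in the list.
- **Criterion 11** is a catch-all for other medical or psychiatric conditions "that may increase the risk of study participation or, in the investigator's judgment, make the participant inappropriate for the study".

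The opening of Section 5 bears on both points. It says "All relevant medical and nonmedical conditions should be taken into consideration when deciding whether a particular participant is suitable for this protocol", and also "Prospective approval of protocol deviations to recruitment and enrollment criteria, also known as protocol waivers or exemptions, is not permitted".

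**The concern.** Section 2.3.1 supports the benefit/risk conclusion and forms part of the protocol that the ethics committee approves. Its reader is told that two groups cannot enter the study. The list that decides entry does not name the first group and names only part of the second.

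Two sites, or two investigators at this one site, could follow the protocol in good faith and decide differently on the same person. One who works from the named conditions could randomize someone whom Section 2.3.1 describes as excluded. One who reads criterion 11 broadly would turn that person away. Section 5 forbids waivers of enrollment criteria, but the text does not settle whether such an enrollment would breach a criterion at all. Section 9.4.5 generally keeps medical history as source data outside the study database, so a later check from the database may not show it.

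Retinopathy is relevant to the people enrolled. Section 2.2 lists it among the complications whose risk rises in poorly controlled T2DM, and the study recruits people inadequately controlled on metformin, with HbA1c from 7.0% to 10.5% (Sections 4.1 and 5.1).

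**Working it through.** No formula applies; this is a check of one part of the text against another. The inputs are the 7 study-intervention rows of Section 2.3.1, inclusion criteria 1 to 6 (Section 5.1), exclusion criteria 1 to 25 (Section 5.2), and Appendix 7, to which criterion 12 refers.

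**Step 1. Could a criterion have been blacked out?** The criteria in Section 5.2 run from 1 to 25 without a gap, and the list carries no redaction mark. The absence of an eye criterion is therefore not a redaction effect.

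**Step 2. Match each risk row to a criterion.**

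| Risk row in 2.3.1 | Entry restriction cited | Counterpart | Match | Other mitigation in the row |
|---|---|---|---|---|
| Thyroid C-cell tumors | Personal or family history of MTC or MEN2 | Criterion 6 | Yes | Thyroid function tests |
| Renal impairment | Below 60 mL/min/1.73m² | Criterion 18 (eGFR) | Yes | BUN, creatinine, eGFR |
| Hypoglycemia | Insulin and sulfonylureas prohibited | Criterion 12 with Appendix 7; also inclusion criterion 2 | Yes | Glucose monitoring |
| Pancreatitis | Acute, or any history | Criterion 7: acute, or history of chronic | Partial | Amylase and lipase |
| Retinopathy | Known active proliferative retinopathy and/or macular edema | None of 25 names an eye condition | No | None listed |
| Gastrointestinal reactions | None | – | – | – |
| Placebo arm | None | – | – | – |

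Five rows rely at least partly on an entry restriction and 2 do not (5 + 2 = 7). Of the 5, 3 are matched, 1 is matched in part and 1 is not matched (3 + 1 + 1 = 5). Four of the 5 list a further mitigation; retinopathy is the exception. The hypoglycemia row is a ban on concomitant drugs rather than an entry exclusion in so many words. Without it the count is 2 matched, 1 partial and 1 unmatched out of 4, and the conclusion is the same.

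**Step 3. Compare the two pancreatitis texts.** In criterion 7 the words for history attach only to chronic disease. In Section 2.3.1 they attach to pancreatitis of any kind. The difference is a past acute episode that has resolved: Section 2.3.1 covers it, and criterion 7 on its natural reading does not. Because the Section 2.3.1 sentence claims to report the exclusion criteria, the two texts conflict directly.

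**Step 4. See what the general criteria cover.** For retinopathy, the possible routes are criterion 11, arguably the endocrine category of criterion 1, and the opening of Section 5. For a resolved pancreatitis episode, they are the gastrointestinal category of criterion 1 and criterion 11. Criterion 18 also excludes amylase or lipase above the upper limit of normal, but that is a current laboratory finding and not a history. These routes could exclude such a person, but each depends on interpretation or on an indirect finding.

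**The case against.** The strongest reply is that nobody need slip through. Criterion 11 is itself one of the 25 criteria. Its limb on conditions that may increase risk is grammatically separate from the limb on investigator judgment. An investigator who reads it together with Section 2.3.1 has a textual basis to exclude active retinopathy or macular edema. That is fair, and it means that the enrollment of such a person is possible rather than expected. It does not remove the mismatch: Section 2.3.1 states a flat exclusion, while criterion 11 requires the site to infer one.

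A second reply is that the retinopathy sentence is programme-level wording. It speaks of clinical studies in the plural and does not invoke the exclusion criteria, as the pancreatitis and renal rows do. The thyroid row, however, is also worded for the development program, and its exclusion was carried into criterion 6. The retinopathy exclusion was not.

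A third reply is that the pancreatitis gap is narrow. Acute pancreatitis in criterion 7 has no time limit, criterion 1 can reach a significant past episode, and criterion 18 removes people with raised enzymes. Amylase and lipase are tested at Screening, Day -1, Day 56 and early termination. This stands as to size. What remains is a resolved acute episode with normal enzymes that the investigator judges neither clinically significant nor a source of added risk.

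Finally, the practical risk is said to be small. That also stands: Section 2.3.1 reports no signal for retinopathy and no pancreatitis in the clinical program, and no primary or secondary analysis changes.

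**Conclusion.** The concern holds. Sections 2.3.1 and 5.2 are inconsistent on two entry exclusions: for retinopathy and macular edema no criterion names the condition, and for pancreatitis criterion 7 is narrower than the statement that claims to report it. The point should be fixed because it bears on eligibility and participant safety, and because for retinopathy the exclusion is the only mitigation the row offers.

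Its consequence is limited. About 15 people are planned to receive active drug for about 8 weeks at one site, and the pharmacokinetic results are unaffected. The documents give no prevalence for either condition, so no number of affected participants can be stated.

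Confidence in the mismatch is high. For pancreatitis it rests on the natural reading of criterion 7, in which the reference to history qualifies only chronic disease. Whether anyone would actually be enrolled against Section 2.3.1 depends on how the site applies criteria 1 and 11, and the documents do not settle that.

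**What to change.** Reconcile the two sections by amendment. For each of the two risks, do one of the following:

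- state the exclusion in Section 5.2 as an explicit criterion, in the same words as Section 2.3.1; or
- revise Section 2.3.1 so that it no longer presents the exclusion as a mitigation in this study.

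For pancreatitis, the text should also say whether a resolved acute episode is covered. Where the clinical boundary lies is for the sponsor's clinicians to decide.

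The cost is amendment text and possibly a few more screen failures. No new procedure is needed: the retinopathy statement concerns known history only, and Table 1 already schedules medical history and eligibility review at Screening and Day -2.

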### 2.3.2. Benefit Assessment

Based on the clinical experience of injectable GLP-1R agonists, an oral GLP-1R agonist is expected to improve glucose control, reduce HbA1c levels, diminish food intake, and decrease body weight in patients with T2DM, while avoiding the requirement for subcutaneous injections that accompanies currently available peptidic GLP-1R agonists. As the treatment period of this study is only 8 weeks, clinical benefit to participants with T2DM is unlikely or limited given the short duration of this study and the early stage of development of PF-06882961. This study is designed to generate safety, tolerability, PK CCI data in Chinese T2DM participants for further clinical development.

### 2.3.3. Overall Benefit/Risk Conclusion

In line with the clinical profile of marketed GLP-1R agonists, the most frequently reported AEs with PF-06882961 administration have been nausea, diarrhea, dyspepsia, headache, and vomiting. In addition, as has been reported for marketed GLP-1R agonists, increases in heart rate have been observed with PF-06882961 administration, with most heart rate values within the normal range.

Considering all available clinical and nonclinical data, the overall benefit-risk profile of PF-06882961 supports further clinical development in patients with T2DM.

## 3. OBJECTIVES , ESTIMANDS, AND ENDPOINTS

Objectives	Estimands	Endpoints
Primary:	Primary:	Primary:

 
To characterize the plasma PK of PF-06882961 following a single oral dose on Day 1 and following multiple, oral doses administered to adult Chinese participants with T2DM.
 
	Not Applicable	
 
Single dose (10 mg): AUC24, Cmax.
 
Multiple dose (40 mg, 80 mg, 120 mg): AUC24, Cmax,ss.
 

Secondary:	Secondary:	Secondary:

 
To evaluate the safety and tolerability of PF-06882961 following a single oral dose on Day 1 and following multiple, oral doses administered to
 
	Not Applicable	
 
Vital signs, Electrocardiograms, Adverse events (e.g. hypoglycemia and hyperglycemia), Clinical safety laboratory assessments.
 

Objectives	Estimands	Endpoints
adult Chinese participants with T2DM.		
CCI [REDACTED]	[REDACTED]	[REDACTED]
[REDACTED]	[REDACTED]	[REDACTED]
[REDACTED]	[REDACTED]	[REDACTED]
[REDACTED]	[REDACTED]	[REDACTED]
[REDACTED]	[REDACTED]	[REDACTED]

